2.5 Study Procedures	
Subject identification Patients will be identified for screening through the renal transplant clinic or nephrology clinics at the University of Maryland.
 
2.5.1 HCV Treatment Arm
 
Screening All patients will be screened at the IHV Clinical Trials Unit infectious disease, or renal transplant outpatient clinic at the University of Maryland. All patients will sign an informed consent as approved by our Institutional Review Board (IRB) prior to study participation. At this visit, all patients will have clinical and research screening labs drawn and a history and physical examination performed. Additional requirements will be genotype testing prior to enrollment, but after transplant for the post-transplantation cohort, and disease staging within 12 months of enrollment by liver biopsy, elastography, or biochemical testing. For those who do not have a genotype or disease staging within the specified time frame, genotyping and elastography will be repeated as part of the study screening work up. Eligibility will be determined based upon these results within 6 weeks of starting the study drugs.
 
Treatment-naïve or treatment-experienced patients who failed prior therapy with pegylated interferon and ribavirin have a 5-10% incidence of having baseline resistance associated mutants (RAVs). Given the reduced efficacy of this regimen in patients with genotype 1a with the presence of baseline NS5A RAVs (58-91% depending upon the methodology vs. 100% for patients with no RAVs), we will screen patients for RAVs in patients with HCV genotype 1a at the time of enrollment (20). Any patient with genotype 1a HCV found to have NS5A RAVs will undergo 16 weeks of therapy according to current treatment guidelines. A complete panel of tests that will be performed during this visit is detailed in Appendix 1.
 
Starting therapy Study drugs will be administered starting on day 0 after a history and physical examination is performed, eligibility is confirmed and clinical and research labs are collected. A complete panel of tests that will be performed during this visit is detailed in Appendix 1.
 
Study visits during treatment Patients will be followed every 4 to 8 weeks while they are receiving study drugs. Patients will be advised about study adherence and monitored for adverse events. A complete panel of tests that will be performed during this visit is detailed in Appendix 1. Study medications will be distributed at visits.
 
Safety and adverse event monitoring At each study visit, study staff will inquire about adverse events that may or may not be related to study drugs. Any unfavorable medical occurrences will be recorded, whether or not considered related to the patient's participation in the research, temporally associated with the patient's participation in the research. Adverse events (AEs) classified as grade 3 or higher will be reported to the principal investigator. Any grade 3 or 4 AEs and all SAEs will be reviewed as they occur by the study team (21). Any AEs occurring more frequently than expected will be reported to the IRB.
 
Principal Investigator shall forward to Merck's Global Safety group, any SAE or Suspected Unexpected Serious Adverse Reaction (SUSAR), including, but not limited to, all initial and follow-up information involving any study subject in the study. Notification shall be in the


form of a completed CIOMS I/MedWatch within two (2) business days of learning of the information. SAE reports and any other relevant safety information are to be forwarded to Merck's Global Safety group [contact]. SAE and Reportable New Information will be reported to the IRB as per University policy.

All reports of Study Drug exposure during pregnancy or lactation, whether associated with an AE or not, must be reported to Merck's Global Safety group in accordance with the timelines and contact information for an SAE. Principal Investigator shall follow pregnancies to term to obtain the outcome of the pregnancy. The outcome of the pregnancy shall be forwarded to Merck's Global Safety group.

Clinical labs will also be drawn at these visits. There is a known, defined drug interaction between grazoprevir and tacrolimus causing an increase in tacrolimus levels of approximately 40%, as documented in the package insert (22). Levels of immunosuppressive agents will also be determined at these visits as clinically indicated. The need for dose modification of the patient's immunosuppression in the time between visits will be recorded.

End of treatment visit

Patients will be seen 12 weeks after starting study drugs (and 16 weeks in the case of genotype 1a patients with baseline NS5A RAVs) for an end of study visit. Patients will also be counseled about study adherence and we will inquire about adverse events. A complete panel of tests that will be performed during this visit is detailed in Appendix 1.

Post treatment follow up visits

Patients will be followed 12 weeks after they complete treatment. A complete panel of tests that will be performed during this visit is detailed in Appendix 1.

Additionally, patients may be enrolled in an ongoing study titled "A prospective cohort study to assess treatment efficacy in chronic hepatitis C mono-infection and co-infection with HIV" (HP – 00063362), to monitor longer-term outcomes. Outcomes including graft survival and episodes of rejection will be monitored by periodic medical record abstraction.

Early termination or treatment discontinuation

Patients who discontinue HCV therapy prior to 12 weeks will be followed at post-treatment week 4 and post-treatment week 12. HCV VL, safety labs and hepatic panel will be performed at these visits. A complete panel of tests that will be performed during this visit is detailed in Appendix 1.

2.5.2 Host Response Measurement

Determination of Interferon stimulated gene expression associated with HCV suppression

PCR. ISG expression rapidly shuts down with initiation of DAA therapy in HCV infected subjects. We would like to evaluate the effectiveness of the host response to DAA therapy in pre- and post-transplant (immunosuppressed) patients by evaluating the changes in ISG expression observed in the two groups of patients before and 4 weeks after completion of HCV therapy.

Expression analysis of select genes will be performed with predesigned or custom TaqMan assays individually or assembled into custom-designed 96-well plates or 384-well microfluidic cards (Life Technologies). Total RNA isolated from paxgenes will be reverse transcribed using random primers with the High Capacity cDNA Reverse Transcriptase Kit (Life Technologies). 1–25 ng RNA will be used for each qRT-PCR reaction. Gene expression will be determined as Ct based on 40 PCR cycles. For statistical analysis,

undetectable expression will be assigned a minimal detectable level with Ct of 40. Expression of *GAPDH* will be used as an endogenous control. Relative expression of targets normalized by *GAPDH* expression (ΔCt) will be calculated as $Ct_{GAPDH} - Ct_{\text{target}}$, with conversion and display relative to *GAPDH* expression by $2^{\Delta Ct}$. $\Delta\Delta Ct$ values, used to calculate changes in expression between samples or groups of samples, will be calculated as $\Delta Ct_{\text{sample A}} - \Delta Ct_{\text{sample B}}$, then converted to a fold change by $2^{-\Delta\Delta Ct}$. Relative expression of individual ISGs FNs in blood will also be calculated as a percent of the sum of the total measured ISGs ($[2^{\Delta Ct} \text{ of each individual ISG} / \text{total } 2^{\Delta Ct} \text{ of all measured ISGs}] \times 100$). 384-well microfluidic cards will be run on a 7900HT Fast Real-Time PCR System (Life Technologies).

Cytokine and Chemokine ELISA. IP-10 is the most studied soluble ISG that has been associated with response to therapy. The expression of IP-10 is rapidly shut down with initiation of DAA therapy in HCV infected subjects and a higher pre-treatment IP-10 level has been associated with a poorer response to therapy. We would like to evaluate the effectiveness of host response to DAA therapy in pre- and post-transplant (immunosuppressed patients) by evaluating the fold changes in IP-10 and other proinflammatory/chemotactic cytokine expression observed in the two groups of patients before and 4 weeks after completion of HCV therapy.

Whole blood will be allowed to clot in for at least 60 minutes prior to centrifugation at 1,700 g for 15 minutes. Serum will be collected and aliquoted prior to freezing at -80°C. After thawing, serum will be centrifuged at 1,450 g for 10 minutes, and the supernatant will be used for ELISA. Quantitation performed with multiplex (Chemokine 9-plex, Proinflammatory 9-plex) assays that include CXCL10 (MesoScale Discovery). Plate-to-plate variability of pooled samples will be used for normalization across experiments. All samples will be run as technical duplicates, and averages will be used for data analysis.

Determination of HCV specific CD4 and CD8 T cells by ELISPOT

We have previously described an augmentation of HCV-specific T-cell responses with DAA therapy being associated with achieving an SVR 12. HCV specific T-cell phenotype and function will be characterized as previously described and measured before and at SVR 12.

In brief, peripheral T-cells will be isolated from PBMCs by Ficollhypaque density gradient separation and be stimulated with pooled HCV genotype specific peptides. For this experiment, we will use HCV 15-18-mer peptides with 11 or 12 amino acid overlaps spanning the entire HCV polyprotein and reconstituted in 5% sterile dimethylsulphoxide (DMSO), pooled consecutively into twenty-one groups and aliquoted until use. The number of HCV-responsive IFN- γ -producing PBMCs will be quantified by a standard ELISPOT assay (BD Biosciences), in which 96 well ELISPOT plates are coated with anti-IFN- γ biotinylated capture antibody and incubated overnight at 4°C. Plates will be blocked using a lymphocyte medium, and PBMCs will be allowed to rest for 6 hours at 37°C. PBMCs will then be plated between 250,000- 400,000 cells per well with either phytohaemagglutinin (PHA) as a positive control (5 mg/ml), DMSO as a negative control (0.05%), or pooled HBV peptides (3 mg/ml/peptide). All cultures will be performed in duplicate. After incubating for 12 hours at 37°C, cells will be removed, and plated with streptavidin detection antibody, enzyme conjugate, and substrate. The plates will then be air dried in the dark overnight, and developed spots will be enumerated using an ELISPOT plate reader.

2.6 Study Duration	We anticipate the entire study duration to be 24 months. The duration per study subject enrolled will be 30 to 34 weeks depending on their treatment duration. This will include 6 weeks of screening, 12 to 16 weeks of therapy, and 12 weeks of follow up to determine SVR 12 (Figure 1).
---------------------------	---

	
After the initial 30-34 weeks, patients will be enrolled in our ongoing HCV treatment cohort study (HP – 00063362). Using this long term prospective cohort study, we will be able to follow our patients' longer-term outcomes through medical record abstraction.


2.7 Statistical Analysis and Sample Size Justification
	
Data analysis will be completed by the study biostatistician.
 
Primary Endpoints
 
Primary Objective 1. The primary endpoint for this objective will be the measurement of host immune responses using ISG expression including IP-10 levels, and HCV specific T-cell responses. ISG expression and IP-10 levels will be measured before and 4 weeks after completion of therapy. HCV specific T-cell responses will be measured before and during SVR 12 (12 weeks after completion of the study medications).
 
Primary Objective 2. The primary endpoint for this objective will be the measurement of SVR 12. This will be measured at study week 24/28, or 12 weeks after completion of the study medications.
 
Secondary Endpoints
 
Secondary Objective 1. We will assess the safety of the medications using adverse event monitoring. The primary endpoint for this objective will be the presence of any severe adverse event. A secondary endpoint will be the early discontinuation of the study medications. This will be assessed at the study visits weeks 0, 4, 8, and 12. Based upon prior trials with these investigational drugs, we estimate rate of serious adverse events of about 15% (17).
 
Secondary Objective 2. The primary endpoint for this objective will be episodes of rejection and graft survival for post-transplant patients after treatment and will be recorded via medical record abstraction as part of their enrollment in the ongoing prospective cohort study to assess treatment efficacy in chronic hepatitis C (HP – 00063362).
 
Research data will be collected and managed using REDCap (Research Electronic Data Capture) hosted at the University of Maryland, which is a secure, web-based application to support data capture for research studies. All of these variables will be entered into REDCap by study staff at the end of each study visit based upon the labs obtained, patient questionnaires, and interim records reviews, and after the initial 30 to 34 weeks of the study based upon medical records reviews.
 
Statistical Methods
 
Clinical treatment arm
 
All statistical analyses will be based on an intention-to-treat model, including all enrolled patients who received at least one dose of study medication. Both the primary efficacy and safety endpoints will be based on the proportion of patients with SVR 12 and severe adverse events, respectively, with point estimates and 95% confidence interval. Both primary efficacy and safety endpoints will be compared to a non-transplant, HCV-infected historical control group by using two-sided, exact one-sample binomial test at a significance level of 0.05. Demographic and baseline characteristics will be summarized using standard descriptive statistics overall and by patient cohort. Univariate logistic regression will be performed to identify baseline factors associated with SVR 12 at a significance level of 0.05.
 
Measurement of host immune response


	
Mann-Whitney or Wilcoxon matched-pairs signed rank test will be used for 2-group comparisons, and a linear mixed-effects model will be used for multigroup longitudinal comparisons with fixed effects for group (SVR versus relapse), time, and group/time interaction. A significant group/time interaction would indicate that the 2 groups had different patterns over time. A class variable will be used for time to allow an arbitrary average time pattern within a group. In addition to fixed effects summarizing average group responses over time, the model will accommodate random, patient-specific deviations in intercept and time effects. Correlations will be assessed by nonparametric Spearman rank correlation. Spotfire S+ 8.2 (TIBCO), Prism 6.0 software (GraphPad), and SAS 9.3 (SAS Institute, Inc.) will be used for statistical analysis and data presentation using a p-value of 0.05 to indicate statistical significance.
 
Power/Sample Size:
 
This is a pilot, prospective clinical trial comparing the host immune response using ISG expression, including IP-10 levels, and HCV specific T-cell responses between a historical, non-transplant cohort of 25 patients from IRB approved studies previously conducted at the IHV and post-renal transplant (immunosuppressed) patients and its association with SVR 12. The study team will perform an interim data and safety evaluation for the efficacy, safety, and tolerability of grazoprevir and elbasvir therapy. Data analysis will focus on the clinical efficacy endpoint of SVR 12 with secondary analysis looking at the relationship of the host immune response markers with the primary endpoint of SVR 12 in both groups.
 
We anticipate enrollment of 25 patients in this arm of the study. This will be compared to a historical control group of 25 patients with stored blood samples from previous IRB approved clinical trials conducted at the IHV.
 
We anticipate a SVR 12 of greater than 90% in the grazoprevir plus elbasvir treatment group post-renal transplantation. With 50 participants (25 in this study and 25 historical controls), the study will be able to estimate the difference in SVR12 proportions to within ± 0.18 (Table 2). Table 2 shows a substantial gain in precision by increasing the sample size from 15 per arm to 25 per arm; however, the effect diminishes beyond 25.
 
Table 2: Sample Size Calculation for SVR12
 
  
 N per arm	15	20	25	30	50	
   
 Accuracy to within \pm	0.24	0.20	0.18	0.17	0.13	
  
	N per arm	15	20	25	30	50	Accuracy to within \pm	0.24	0.20	0.18	0.17	0.13
N per arm	15	20	25	30	50								
Accuracy to within \pm	0.24	0.20	0.18	0.17	0.13								
2.8 Specific Drug Supply Requirements	
We request study drug supply from Merck Inc. for all study subjects. The study drugs will be received and distributed by [name], RPh, through the UMD investigational drug pharmacy. The study drugs will be stored under the conditions specified by the manufacturer. Packaging and labeling will be done by Merck. At the study's conclusion the remaining investigational product will be disposed of according to the ICH/GCP guidelines and our institution's policies.
												
2.9 Adverse Experience Reporting	
2.9.1 Overview
 
Adverse experience reporting will be performed per study agreement at each study visit. During each clinical evaluation with the patients, information regarding adverse events and adverse reactions will be elicited. Any untoward or unfavorable medical occurrences will be recorded, whether or not considered related to the patient's participation in the research. Additionally, patients may be seen at unscheduled visits for a grade 3 or 4 adverse event or any unexpected adverse event or potential toxicity.
												

Adverse events (AEs) classified as serious or grade 3 or higher will be reported to the principal investigator. Any grade 3 or 4 AEs and all SAEs will be reviewed as they occur by the study team. Any AEs found to be occurring above the level expected by the study team will be reported to the IRB and study sponsor.

For this study, patients may have expected AEs related to transplantation in the post-transplantation arm or related to renal failure in the pre-transplantation arm. This protocol will record all AEs possibly related to the treatment of HCV as defined by the Office for Human Research Protections (OHRP) (21).

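### The ISG fold-change formula in section 2.5.2 returns sample B relative to sample A, and the plan does not say which sample is the reference, so the direction of the reported change is not fixed

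*Combined protocol and SAP*

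**What the plan says.** The PCR part of section 2.5.2 sets out four steps.

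- ΔCt is the GAPDH Ct minus the target Ct, "with conversion and display relative to *GAPDH* expression by $2^{\Delta Ct", with a positive exponent.
- ΔΔCt "values, used to calculate changes in expression between samples or groups of samples, will be calculated as" ΔCt of sample A minus ΔCt of sample B.
- That difference is "then converted to a fold change by $2^{-\Delta\Delta Ct", with a negative exponent.
- The expression of each gene "will also be calculated as a percent of the sum of the total measured ISGs", again with a positive exponent on ΔCt.

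The same part says that "undetectable expression will be assigned a minimal detectable level with Ct of 40", and gives the purpose as "evaluating the changes in ISG expression observed in the two groups of patients before and 4 weeks after completion of HCV therapy". Section 2.7, under Primary Endpoints, makes ISG expression part of the endpoint for Primary Objective 1: "ISG expression and IP-10 levels will be measured before and 4 weeks after completion of therapy". Under Power/Sample Size, section 2.7 also describes a "secondary analysis looking at the relationship of the host immune response markers with the primary endpoint of SVR 12 in both groups". Neither section says which sample or group is A, which is B, or which is the reference.

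**The concern.** A negative exponent on ΔΔCt gives A relative to B when ΔCt is the target minus the reference gene. This plan defines ΔCt the other way round and follows that definition in its other two conversions. The fold-change step is the only one whose exponent has the opposite sign. An analyst who takes A as the later sample, or as the transplant cohort, and applies the formula as written would report a fall as a rise.

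The formula is meant for both samples and groups of samples. It therefore covers the before/after change and any fold change between the transplant and historical cohorts. The direction of that change is the substance of the ISG part of Primary Objective 1. The plan as written allows two opposite reports from the same data.

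**Working it through.** **Inputs from section 2.5.2**

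- ΔCt = Ct(GAPDH) − Ct(target)
- Expression relative to GAPDH: E = 2^(ΔCt)
- ΔΔCt = ΔCt(A) − ΔCt(B)
- Fold change as written: 2^(−ΔΔCt)

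The plan states no numerical fold change, so there is no figure of its own to reproduce.

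**Step 1: orientation of the scale.** A larger ΔCt means more expression. The rule for undetectable targets agrees: a Ct of 40, the last of the 40 cycles, gives the most negative ΔCt and so the lowest E.

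**Step 2: algebra.**

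- E(A)/E(B) = 2^(ΔCt(A) − ΔCt(B)) = 2^(+ΔΔCt)
- As written: 2^(−ΔΔCt) = 2^(ΔCt(B) − ΔCt(A)) = E(B)/E(A)

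The written formula therefore always returns B relative to A. When A has the higher expression, ΔΔCt is positive and the fold change is below 1.

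**Step 3: one example.** The documents give no Ct values, so these are assumed: GAPDH 20 at both times, target 25 before and 28 after.

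- ΔCt before = 20 − 25 = −5; ΔCt after = 20 − 28 = −8
- True after/before ratio = 2^(−8) / 2^(−5) = 2^(−3) = 0.125
- As written with A = after: ΔΔCt = −8 − (−5) = −3, and 2^(3) = 8
- As written with A = before: ΔΔCt = −5 − (−8) = 3, and 2^(−3) = 0.125
- Positive exponent with A = after: 2^(−3) = 0.125

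**Step 4: range of assumed falls.** The GAPDH Ct cancels when it is equal in both samples, so only the shift matters.

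| Fall in cycles | True after/before | As written, A = after | As written, A = before |
|---|---|---|---|
| 1 | 0.5 | 2 | 0.5 |
| 2 | 0.25 | 4 | 0.25 |
| 3 | 0.125 | 8 | 0.125 |
| 5 | 0.031 | 32 | 0.031 |

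**Step 5: what the formula reaches.** Taking reciprocals reverses the order of the fold changes.

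- A Mann-Whitney comparison of fold changes, or a signed-rank test on their logarithms, keeps its two-sided p-value if one convention is used throughout.
- A Spearman correlation that uses the fold change keeps its size and changes sign. Section 2.7 does not name the variables to be correlated.
- Matched-pairs tests and the mixed model on per-visit values do not use the formula. Nor do the 2^(ΔCt) display, the percent-of-total measure, the IP-10 immunoassay, ELISPOT or SVR12.

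**The case against.** The strongest reply is that this is an unlabelled convention and not a wrong calculation. The other two conversions act within one sample, whereas a fold change compares two, and its sign depends on the order of subtraction. A negative exponent simply means B over A, which is legitimate once labelled. Sections 2.5.2 and 2.7 both name the sample before treatment first. If A is the first-named sample, the formula gives after relative to before, as wanted. An inverted ratio would also clash with the plan's expectation that ISG expression falls with therapy and with its own 2^(ΔCt) display, and recalculation would settle the matter. Finally, the point about the sign rests on one superscript minus read from a PDF by a program.

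Much of this stands. The inversion is conditional, it can be detected, and the sign needs checking. But word order is not an assignment of A and B, and the ordinary reading of A minus B is A relative to B, for which the formula gives the reciprocal. Expectation is also an unsafe check. Section 2.2 links viral clearance on treatment to lower ISG expression, but SVR to higher ISG expression in the liver, so a reported rise need not look wrong. If the minus sign proves to be a reading error, the reference would still be unnamed.

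A reader might go further and infer that the ISG results will be reversed, that the two cohorts will be handled in opposite ways, or that undetectable samples will produce enormous false rises. The documents do not support these readings. They assign neither sample, say nothing of different conventions by cohort, and give no Ct values.

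**Conclusion.** The point holds as a sign mismatch combined with a missing definition. On the plan's own scale the written formula gives B relative to A. The reported ISG fold change is the exact reciprocal of the true one if A is the post-treatment or transplant sample, and correct if A is the baseline or historical sample. For assumed falls of 1 to 5 cycles, the reversed figures would be 2 to 32 in place of 0.5 to 0.031.

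The algebra is certain for the text as transcribed. Whether any result would be reversed depends on an assignment that the plan does not make. The consequence is limited to the direction and size of the ISG fold change and the sign of any correlation built on it. It should be settled before analysis because the quantity belongs to a primary objective and the direction should not be chosen after the data are seen. It does not threaten the trial's efficacy conclusion, its sample size or its other immune measures.

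**What to change.** Check the exponent against the source document. Then do one of the following in section 2.5.2:

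- write the fold change as 2^(+ΔΔCt), with A the post-treatment (or transplant) sample and B the baseline (or historical) sample; or
- keep 2^(−ΔΔCt) and state that A is the baseline or reference sample.

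The two are equivalent. State that the chosen convention applies to both cohorts. The cost is one sentence, with or without one change of sign, and nothing changes in samples, assays or sample size.

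As a separate item, the ELISPOT paragraph of section 2.5.2 describes HCV peptide pools but names HBV peptides in the plating step. These need to be reconciled; that mismatch plays no part in this point.

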- Have stable renal function for one month (30 days) prior to enrollment
- Have Chronic HCV infection prior to transplantation
 - Documented HCV viremia \geq 1,000 IU/ml at screening
 - Either documented HCV Ab positivity or HCV viremia \geq 1,000 IU/ml at least 6 months prior to enrollment
- Documented genotype 1 HCV infection prior to enrollment and after their transplant in the post-transplantation cohort
- HCV disease staging within 12 months prior to enrollment by liver biopsy, transient elastography, or biochemical testing
- Be able to give informed consent and comply with study guidelines
- Women of childbearing age will be required to have a negative pregnancy test at enrollment and use birth control throughout the duration of treatment.
- Patients will have undergone renal transplantation no greater than five years prior to enrollment, and will be followed in our University's nephrology and infectious disease clinic. They will all have stable renal function at the time of enrollment.

Exclusion criteria

- Documented positive HBsAg, and/or HBV DNA prior to enrollment
- Any prior exposure to HCV protease inhibitor therapy
- HIV co-infection if on a protease inhibitor, etravirine or efavirenz based regimen or elvitegravir/cobicistat/emtricitabine/tenofovir disoproxil fumarate
- Increase in creatinine of 15% or greater within one month (30 days) of the screening visit
- Evidence of HCC at the time of enrollment
- Liver disease caused by an etiology other than HCV
- F4 or decompensated cirrhotic patients
- Child Pugh class B or C
- AST or ALT >350 within 6 months prior to enrollment
- Albumin $< 3\text{g/dL}$ at the time of enrollment
- Platelet count $< 75,000$ at the time of enrollment
- History of clinically significant allergy or adverse event with protease inhibitors
- Evidence of the acquisition of HCV at the time of or after transplantation
- Pregnant or breastfeeding women
- Cyclosporine; St. John's Wort; Efavirenz; Phenytoin; Carbamazepine; Bosentan; HIV Protease Inhibitors; modafinil; Ketoconazole; or Rifampin use within 7 days of enrollment
- Coadministration of more than 20 mg atorvastatin; 10 mg rosuvastatin; 20 mg of fluvastatin, lovastatin or simvastatin

	RAV testing (for NS5A positions 28, 30, 31 or 93) will be performed for all patients with HCV genotype 1a infection at the time of enrollment as per clinical recommendations (20).

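### The ELISPOT text for the primary T-cell endpoint contradicts itself on antigen and cell input, and states no CD4/CD8 step and no scaling of counts to cells plated

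*Combined protocol and SAP*

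**What the plan says.** Section 2.1 makes the HCV-specific T-cell response part of Primary Objective 1. Under Primary Endpoints, section 2.7 sets the timing: "HCV specific T-cell responses will be measured before and during SVR 12". Neither place asks for separate CD4 and CD8 results.

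The assay is described in section 2.5.2 under the heading "Determination of HCV specific CD4 and CD8 T cells by ELISPOT". Its introduction says "HCV specific T-cell phenotype and function will be characterized as previously described and measured before and at SVR 12", with no method given at that point. The short description that follows opens: "peripheral T-cells will be isolated from PBMCs by Ficollhypaque density gradient separation and be stimulated with pooled HCV genotype specific peptides". It goes on to overlapping HCV peptides that cover the whole polyprotein, in twenty-one pools, and to a count of IFN-gamma-producing PBMCs that respond to HCV.

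At the plating step, "PBMCs will then be plated between 250,000- 400,000 cells per well". The conditions listed there are PHA as positive control, then "DMSO as a negative control (0.05%), or pooled HBV peptides (3 mg/ml/peptide". All cultures are in duplicate.

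The exclusion criteria in section 2.3 include "Documented positive HBsAg, and/or HBV DNA prior to enrollment".

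**The concern.** The plating sentence is the only one that lists the contents of the wells. Its single test antigen is from a different virus than the one the endpoint concerns, and it mentions no HCV well. No objective concerns HBV immunity, and patients with HBsAg or HBV DNA are excluded, so the plan gives no reason for HBV wells. This is a working step of a primary-endpoint assay, not background text.

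Three further gaps sit in the same description:

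- The cell input changes from T-cells to PBMCs.
- The heading promises a subset result for which no step is stated.
- The read-out is a number of producing cells, while the number of cells plated may vary from well to well and no denominator is given.

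What is at stake is whether the T-cell part of Primary Objective 1 is defined well enough to be run in one way, compared between 25 recipients and 25 historical controls with stored samples, and reported without claiming more than the assay shows.

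**Working it through.** The plan states no figure to reproduce. The check is mainly a comparison of statements, with one short calculation.

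**Antigen (2.5.2, ELISPOT text)**

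| Statement | Virus named |
|---|---|
| Stimulus in the opening sentence: "be stimulated with pooled HCV genotype specific peptides" | HCV |
| Peptide set, twenty-one pools | HCV |
| Response that is counted | HCV |
| Test antigen in the plating sentence | HBV |

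Three statements name HCV and one names HBV. The heading, the objective in 2.1 and the endpoint in 2.7 also name HCV. The document describes no HBV peptide set.

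**Cell input.** The opening sentence isolates T-cells from PBMCs. The cells then rested, plated and counted are all called PBMCs. The text conflicts and does not settle which is meant.

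**CD4/CD8.** The steps given are stimulation, plating, incubation, detection and spot counting. None selects, depletes or stains for CD4 or CD8. A single IFN-gamma spot count obtained this way cannot be assigned to either subset.

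**Scaling.** The inputs are the lower and upper cells per well from the plating sentence, 250,000 and 400,000. For a fixed true frequency f of responding cells,

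expected spots = f × cells plated.

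- Ratio of upper to lower: 400,000 / 250,000 = 1.6.
- Shortfall at the lower input: 1 − 250,000/400,000 = 0.375, or 37.5% fewer spots.

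To illustrate with an assumed f of 100 per 10^6: 100 × 0.25 = 25 spots at the lower input and 100 × 0.40 = 40 at the upper. Divided by cells plated, both return 100 per 10^6.

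The other two host-response assays in 2.5.2 do state their normalisation. The PCR uses GAPDH as endogenous control and sets undetectable values to a Ct of 40. The cytokine assay uses pooled samples across plates and averages its duplicates. For ELISPOT no denominator, background subtraction or rule for combining pools is stated, although DMSO wells are planned.

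**The case against.** The strongest reply is that HBV is plainly a one-letter slip. Everything around it says HCV, no HBV peptides are described, and HBV-positive patients are excluded. A laboratory would have to ignore the stimulation and peptide sentences to run the wrong antigen. That reading is the most likely one. A reader might infer from the plating sentence that the trial, as written, does not measure an HCV response at all; the three HCV statements in the same text do not support that. What remains is that an operative step names the wrong antigen and the plan must state one.

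Second, the CD4/CD8 split is not part of the primary endpoint, and the text presents itself as a summary of a method described elsewhere. This also stands. The conflict is with the assay's own heading, and the documents do not show that the trial cannot separate the subsets. They show only that no step for doing so is stated.

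Third, silence on scaling is not a plan to analyse raw counts, and 1.6 is the extreme of the permitted range. Both points are correct. The factor applies only if counts are left unscaled and inputs sit at opposite ends. The gap is still that the endpoint has no stated unit.

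Finally, a reader might infer that immunosuppressed recipients would yield fewer cells, so that raw counts would fall in the direction of an immunosuppression effect. The documents give no cell yields for recipients or for the stored control samples. The direction could be either way or nil, and no claim about it should be made.

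**Conclusion.** The concern holds as an internal contradiction plus an incompletely defined read-out.

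- **Certain from the text:** the plating step names HBV where the rest of the assay description names HCV; T-cells and PBMCs are both given as the cell input; no CD4/CD8 step is stated despite the heading; and no scaling is stated for an input range of 250,000 to 400,000 cells per well.
- **Conditional:** a difference of up to 1.6-fold (37.5% fewer spots at the low end) between samples with equal true frequency. This assumes that counts are analysed unscaled, that inputs lie at the two extremes, and that spots are proportional to cells plated.

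As described, the assay supports a statement about the total IFN-gamma response only. The correction matters because the assay serves a primary objective.

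**What to change.** In section 2.5.2:

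1. At the plating step, replace the HBV peptides with the twenty-one HCV pools already described. For any samples already run, confirm from laboratory records which peptides were used.
2. State one cell input, T-cells or PBMCs, and use that term throughout.
3. Define the read-out as HCV-specific spots per 10^6 cells plated after DMSO subtraction. For each pool: (mean spots in the duplicate pool wells / cells per well − mean spots in the DMSO wells / cells per well) × 10^6. State how pools are combined, for example by summing over the twenty-one. Record the cells plated for every well, and repeat the definition under Primary Endpoints in 2.7.
4. Either state the CD4/CD8 method already in use, or limit the heading and all conclusions to the total IFN-gamma T-cell response.

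The HCV pools, DMSO wells and duplicates are already planned, so the cost is wording, recording the cells plated, and a check of records if samples have been run. If no subset method is in use, the price is giving up the CD4/CD8 claim, which the endpoint in 2.7 does not require.
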